Tumor assessments will be performed at post-baseline timepoints (every 8 weeks (\pm 7 days) after Cycle 1 Day 1, or as indicated if disease progression is suspected clinically) using the same imaging modality (eg, contrast-enhanced CT, MRI scan) and under the same operating conditions as the Screening/Baseline scans.

A brain scan (CT with contrast or MRI [pre- and post-gadolinium]) will be performed at Screening, and as clinically indicated to assess potential for CNS disease and/or metastases. For subjects with a history of protocol-eligible treated brain metastases, a brain scan will be required at all tumor assessment timepoints. For all subjects, a follow-up brain scan must be performed to confirm CR within 1 week following response confirmation, or if clinically indicated.

A bone scan using whole body bone MRI, ⁹⁹m-technetium based bone scans, or ¹⁸F-sodium fluoride positron emission tomography will be performed during screening to establish a baseline (a historical bone scan performed within 6 weeks before Cycle 1 Day 1 is acceptable), approximately every 24 weeks (in conjunction with a scheduled tumor assessment visit), and as clinically indicated. Lesions identified on bone scans should be followed with cross-sectional imaging.

Tumor assessments will be performed at Screening and every 8 weeks (\pm 7 days) after Cycle 1 Day 1 (ie, 8, 16, 24 weeks) or as indicated if disease progression is suspected clinically.

All responses must be confirmed no less than 28 days following the initial assessment of response. In order for stable disease to be considered the best overall response, it must occur \geq 7 weeks following the first dose of study drug.

Subjects who discontinue study treatment without disease progression will continue to have tumor assessments (recorded up to the data cutoff date for the primary analysis) as per the Schedule of Assessments until disease progression, death, or initiation of another anticancer therapy, whichever occurs first, unless the study is terminated.

Pharmacokinetic Assessments

In dose escalation:

- On Cycle 1 Day 8, PK (palbociclib) blood samples to determine plasma concentrations of palbociclib will be collected at predose (within 1 hour before administration of study drug) and 1 (±10 minutes), 2 (±15 minutes), 4 (±20 minutes), 6 (±30 minutes), 8 (±30 minutes), and 24 hours (±60 minutes, must be before administration of the next day's dose of study drugs) postdose. These windows apply to PK sampling on other days.
- On Cycle 1 Day 21, PK (palbociclib and H3B-6545) blood samples to determine plasma concentrations of palbociclib and H3B-6545 will be collected at predose and 1, 2, 4, 6, 8, and 24 hours postdose.
- On Cycle 1 Day 28, PK (H3B-6545) blood samples to determine plasma concentrations of H3B-6545 will be collected at predose and 1, 2, 4, 6, 8, and 24 hours postdose.
- During the treatment phase, PK (palbociclib and H3B-6545) blood samples to determine plasma concentrations of palbociclib and H3B-6545 will be collected at predose in conjunction with each tumor assessment, that is, approximately every 8 weeks until end of treatment (EOT) or data cutoff date for the primary analysis, whichever is earlier.
In dose expansion:

- On Cycle 1 Day 21, PK (palbociclib and H3B-6545) blood samples to determine plasma concentrations of palbociclib and H3B-6545 will be collected at predose (within 1 hour before administration of study drug) and 1 (±10 minutes), 2 (±15 minutes), 4 (±20 minutes), 6 (±30 minutes), 8 (±30 minutes), and 24 hours (±60 minutes, must be before administration of the next day's dose of study drugs) postdose. These windows apply to PK sampling on other days.
- During the treatment phase, PK (palbociclib and H3B-6545) blood samples to determine plasma concentrations of palbociclib and H3B-6545 will be collected at predose in conjunction with each tumor assessment, that is, approximately every 8 weeks until progression.

Pharmacodynamic, Pharmacogenomic, and Other Biomarker Assessments In dose escalation and expansion:

- At baseline (during screening), pretreatment fresh biopsies or archival tumor tissue (the tumor sample must have been collected after the most recent progression or recurrence) will be obtained from all subjects. If a subject consents to collection of fresh baseline biopsy, it may be acquired any time during the Screening period, before administration of the 1st dose of study drug on Cycle 1 Day 1. If collection of a biopsy during the screening period poses disproportionate risk to subject's safety, the reason for the contraindication must be documented in source at site. Once documentation detailing risk is captured in the site records, subject may continue screening and if all I/E criteria are met, subject may be enrolled and treated.
- At baseline, Cycle 1 Day 1, Cycle 1 Day 21, Cycle 3 Day 1, and every 8 weeks thereafter (coinciding with CT/MRI tumor assessments schedule until radiological progression), and at EOT (if different from date of progression), whole blood samples for mutation characterization from cell-free DNA (cfDNA) will be collected. Biomarker sample collection will end at the time of the primary analysis data cutoff date.

Safety Assessments

Safety assessments will consist of monitoring and recording the following:

- Physical examination
- ECOG performance status
- Height, weight, and vital signs
- 12-lead ECGs
- ECHO, MUGA scan
- Laboratory assessments including but not limited to hematology, biochemistry, and lipid panel

Bioanalytical Methods

Plasma concentrations of H3B-6545 and palbociclib will be determined using validated highperformance liquid chromatography/tandem mass spectrometry (LC-MS/MS) methods. If appropriate, assessment of plasma concentration for any metabolites of H3B-6545 may be explored.

Statistical Methods

Primary Endpoint

The primary study endpoint is to determine the MTD and/or RP2D.

Secondary Endpoints

- AEs and serious adverse events (SAEs) as well as changes in clinical laboratory values. vital sign measurements and ECG parameters.
- Standard primary PK parameters including, but not limited to, the area under the plasma concentration-time curve from timepoint 0 through the last measurable point (AUC_{0-t}), C_{max} , time of the maximum observed plasma concentration (T_{max}), C_{24} , and ratio of the DDI effect
- ORR, defined as the proportion of subjects achieving a best overall response of confirmed partial or CR (PR+CR)
- DoR, defined as the time from the date of the 1st documented CR/PR until the 1st documentation of disease progression or death, whichever comes first
- CBR, defined as the proportion of subjects achieving a best overall response of confirmed partial or CR, or durable stable disease (duration is at least 23 weeks)
- PFS, defined as the time from the 1st dose date to the date of the 1st documentation of disease progression or death (whichever occurs 1st)
- OS, defined as the time from 1st dose date to the date of death from any cause
- Analysis Sets
- Safety Analysis Set: which will consist of all subjects who receive at least 1 dose of study drug. This will be the analysis set for all safety evaluations except DLT results.
- Full Analysis Set: which will consist of all subjects who receive at least 1 dose of study drug.
- Dose Evaluable Set: which will consist of all subjects who were evaluable for DLT in Phase 1b. This will be the analysis set for DLT results.
- Response-Evaluable Set: which will consist of those subjects who receive at least 1 dose of study drug and have measurable disease at baseline and at least 1 postbaseline tumor assessment. This will be the primary analysis set for efficacy evaluations.
- *Pharmacokinetic Analysis Set:* which will consist of subjects who received at least 1 dose of study drug and all valid plasma concentrations (at least 3 valid concentrations for noncompartmental analysis).

Efficacy Analyses

All efficacy parameters will be summarized descriptively for the Response-Evaluable Set and Full Analysis Set. ORR and CBR will be calculated with exact 95% confidence intervals using the method of Clopper and Pearson. DoR will be calculated for subjects achieving a best overall response of confirmed PR+CR. For DoR, PFS, and OS, medians will be calculated using Kaplan-Meier estimates. DoR, PFS, and OS will be reported in both summary tables and plotted with Kaplan-Meier curve.

Pharmacokinetic Analyses

The plasma concentrations of palbociclib and H3B-6545 will be presented by dose level and day, as the number of subjects with data, geometric mean, mean, standard deviation (SD), median, minimum, and maximum values by nominal sampling timepoint. The PK parameters will include, as applicable, C_{max} (T_{max}), AUC₀₋₂₄ (AUC from zero time to 24 hours), AUC_{0-t} (AUC from zero time to last measurable concentration), AUC_{0-inf} (AUC from zero time to infinity), percentage of AUC that is due to extrapolation from the last measurable concentration to infinity (%AUC_{Extrap}), apparent terminal disposition rate constant (λ_z), apparent plasma terminal elimination half-life, apparent total plasma clearance (CL/F), and apparent volume of distribution (V/F).

The palbociclib and H3B-6545 PK parameters will be tabulated per dose level and day, with the number of measurements, number of non-missing data, mean, SD, median, minimum, maximum, geometric mean, and coefficient of variation (CV%; based on untransformed data).

The DDI effect on each other at steady state will be calculated as summarized appropriately (refer to Section 9.4.7.1).

Pharmacodynamic, Pharmacogenomic, and Other Biomarker Analyses

The baseline tissue biopsies collected will be used to examine potential baseline markers of response. These markers may include but are not limited to ER, PR, RB, Ki67, HER2, gene expression and DNA mutations (using standard technologies like quantitative polymerase chain reaction, immunohistochemistry, and other appropriate technology) along with global transcription levels (RNA sequencing).

The whole blood samples will be analyzed for evaluation of cfDNA as a source of circulating biomarker (DNA mutations). The samples might be used for exploratory analysis for evaluation of response-related and/or safety-related outcomes as well as for potential use in companion diagnostic and drug development, and would be reported separately if conducted.

Exposure-response with biomarkers and/or other efficacy endpoints might be explored as appropriate with a population PK model-predicted exposure values and will be reported separately.

Safety Analyses

The determination of the MTD and/or RP2D will be based on Dose Evaluable Set that consists of all DLT-evaluable subjects. Subjects not evaluable for DLT assessment will be replaced.

All other safety analyses will be performed on the Safety Analysis Set. Safety data will be summarized using descriptive statistics (eg, n, mean, standard deviation, median, minimum, maximum for continuous variables; n [%] for categorical variables). Safety variables include

treatment-emergent adverse events (TEAEs), clinical laboratory parameters, vital signs, and 12-lead ECG results.

Safety will be assessed through the analysis of the reported incidence of TEAEs. The AEs will be coded using the Medical Dictionary for Regulatory Activities, and summarized using system organ class and preferred term. In addition, summaries of SAEs, AEs leading to treatment discontinuation, AEs by maximum National Cancer Institute CTCAE v5.0 grade, and AEs related to study treatment will also be presented by dose level.

Other safety endpoints, including laboratory results, vital signs, and ECG findings, will be summarized for all subjects in the Safety Analysis Set.

Interim Analyses

No formal interim analyses are planned. However, the cumulated safety and efficacy data by dose level will be reviewed periodically by the sponsors and investigators. The continuation of study enrollment will depend on the totality of the efficacy and safety data.

Sample Size Rationale

Depending on the dose levels to be studied in the dose escalation part, approximately 12 to 24 subjects may be treated. Dose expansion will enroll 12 additional subjects at the RP2D. Therefore, the study is expected to enroll approximately 24 to 36 subjects. No formal sample size calculation is performed.

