Subjects in dose expansion may have received up to 2 prior endocrine therapies and up to 1 prior chemotherapy regimen but may not have received a prior CDK4/6 inhibitor in the advanced or metastatic setting.

Subjects who are tolerating therapy and are without progressive disease may receive treatment until progression.

Dose escalation will determine the MTD and/or the RP2D of H3B-6545 in combination with palbociclib. Due to the potential for screen failures and/or a subject discontinuing treatment before completion of the cohort DLT assessment window (non-evaluable for DLT assessment), up to 8 slots will be opened for screening in order to obtain 6 DLT-evaluable subjects (See Section 9.1). In addition, subjects considered screen failures or unevaluable for DLT will be replaced. Each cohort will consist of 6 DLT-evaluable subjects to ensure sufficient safety and PK data are obtained prior to dose escalation. A cycle of treatment will be 28 days.

In the 1st cycle, palbociclib will be administered orally (PO) once daily (QD) on Days 1 to 21 and H3B-6545 will be administered PO QD on Days 9 to 28. In all subsequent cycles, palbociclib will be administered on Days 1 to 21 and H3B-6545 will be administered Days 1 to 28.

A maximum of 4 dose levels are planned, with palbociclib escalated no higher than 125 mg QD and H3B-6545 escalated no higher than 450 mg QD (RP2D).

Dose Level (Cohort)	Palbociclib Dose (mg QD)	H3B-6545 Dose (mg QD)	Number of DLT- Evaluable Subjects
-1	75	300	6
1 (starting dose)	100	300	6
2	125	300	6
3	125	450	6
3b	100	450	6

Dose Escalation Table

DLT= dose-limiting toxicity; QD = once daily.

Subjects will be assigned to a dose level in the order of study entry.

Dose-limiting toxicities (DLTs) will be assessed during the first 28 days starting from the 1st day of adding H3B-6545 to palbociclib (Cycle 1 Day 9 to Cycle 2 Day 8). Subjects who do not receive at least 75% of the scheduled therapy from Cycle 1 Day 9 to Cycle 2 Day 8, for

reasons other than toxicity, will not be considered evaluable for DLT assessment and will be replaced. Disease progression and adverse events (AEs) deemed related to disease progression will not be considered DLTs.

After 6 DLT-evaluable subjects in a cohort have completed the DLT observation period, all available safety data will be reviewed by the Safety Review Committee (SRC) consisting of sponsor personnel and investigators.

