- **Cohort 1:** If none or only 1 subject experienced a DLT, initiate enrollment in Cohort 2. If 2 or more subjects experienced a DLT, initiate enrollment in Cohort -1.
- **Cohort -1:** If none or only 1 subject experienced a DLT, the doses used in Cohort -1 will be considered the RP2D. If 2 or more subjects experienced a DLT, the combination of H3B-6545 and palbociclib at clinically meaningful doses will be considered unfeasible.
- **Cohort 2:** If none or only 1 subject experienced a DLT, initiate enrollment in Cohort 3. If 2 or more subjects experienced a DLT, the doses used in Cohort 1 will be considered the MTD and the RP2D.
- **Cohort 3:** If none or only 1 subject experienced a DLT, doses used in this Cohort will be considered the RP2D. If 2 or more subjects experienced a DLT, consideration will be given to opening cohort 3b depending upon observed toxicity profile.
- **Cohort 3b:** If none or only 1 subject experienced a DLT, doses used in this Cohort and in Cohort 2 could be considered the RP2D. In this case, the SRC will select between Cohort 2 and Cohort 3b for the expansion phase. If 2 or more subjects experienced a DLT, doses used in Cohort 2 will be considered the RP2D.

The MTD is defined as the highest dose at which no more than 1 of 6 subjects experiences a DLT in the dose cohort. The RP2D may not exceed the MTD and will be agreed upon by the SRC based on an integrated evaluation of available safety, clinical benefit, PK, and pharmacodynamics data, for all dose levels tested.

DLTs: Unless considered not related to study drugs, any of the following criteria will qualify as a DLT:

Toxicity	Criteria ^a	
Hematology	- Febrile neutropenia (ANC <1×10 ⁹ /L and fever \ge 38.5 ° C)	
	- Grade 4 neutropenia that does not resolve to Grade ≤ 2 (ANC $\geq 1 \times 10^{9}/L$) within 7 days; use of GM-CSF is allowed	
	- Grade 4 thrombocytopenia (<25.0×10 ⁹ /L)	
	 Grade 3 thrombocytopenia (25.0 – 50.0×10⁹/L) lasting more than 7 days or associated with clinically significant bleeding 	
Vomiting	- CTCAE Grade 4 vomiting	
	- Grade 3 vomiting lasting >72 hours despite optimal antiemetic treatment	
Diarrhea	- CTCAE Grade 4 diarrhea	
	- Grade 3 diarrhea lasting >72 hours despite optimal antidiarrheal treatment	

Electrolytes abnormality	 Grade 4 Grade 3 lasting for more than 24 hours Note: Grade 3 that lasts <24 hours and resolves spontaneously or responds to conventional medical interventions is not considered a DLT. 	
Renal	- Grade 3 or 4 serum creatinine	

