Hepatic	 Grade 3 or 4 bilirubin increase ALT or AST >8 × ULN In absence of liver metastases at baseline and in absence of clinical or radiological evidence of biliary obstruction: ALT or AST >3 × ULN, in conjunction with total bilirubin >2 ×ULN 	
Biochemistry	 Grade 4 Grade 3 lasting more than 7 days, unless considered not clinically significant as per the discretion of the investigator 	
Any other non- hematologic AE	Grade 4 Grade 3 (except diarrhea, rash, nausea, or vomiting lasting ≤72 hours) Any drug-related intolerable Grade 2 toxicity (other than hematological AEs) leading to administration of <75% of the dose during the DLT observation period	

AE = adverse event; ALT = alanine aminotransferase; ANC = absolute neutrophil count; AST = aspartate aminotransferase; CTCAE = Common Terminology Criteria for Adverse Events; DLT = dose-limiting toxicity; GM-CSF = granulocyte– macrophage colony-stimulating factor; ULN = upper limit of normal.

a. Laboratory values that meet criteria listed in this table should be repeated and confirmed within 24 hours of the initial results being reported.

Intrasubject dose escalation: Once a subject has completed Cycle 3 at her assigned dose level of drug, intrasubject dose escalation will be allowed. No more than 2 dose escalations are allowed for any subject. Only subjects who have not progressed on treatment and did not have a dose reduction of either palbociclib or H3B-6545 because of AEs can escalate to the highest dose level that has completed DLT assessment and has been shown to be safe (no more than 1 DLT in 6 subjects). Subjects on the intra-subject dose escalation will not be included in the DLT analysis at the higher dose level.

Dose expansion: An additional 12 subjects will be treated at the MTD/RP2D to further characterize safety, tolerability, and PK and to provide preliminary estimates of efficacy. In Cycle 1, subjects will receive palbociclib PO QD on Days 1 to 21 and H3B-6545 PO QD on Days 9 to 28. In all subsequent cycles, palbociclib will be administered on Days 1 through to 21 and H3B-6545 will be administered Days 1 through to 28.

AEs will be managed by treatment interruption, dose reduction, and/or treatment discontinuation in accordance with the dose modification instructions outlined in the protocol. Treatment will continue until disease progression, development of unacceptable toxicity, or withdrawal of consent.

Number of Subjects

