Any other non- hematologic AE	Grade 4 Grade 3 (except diarrhea, rash, nausea, or vomiting lasting ≤72 hours) Any drug-related intolerable Grade 2 toxicity (other than hematological AEs) leading to administration of <75% of the dose during the DLT observation period

AE = adverse event; ALT = alanine aminotransferase; ANC = absolute neutrophil count; AST = aspartate aminotransferase; CTCAE = Common Terminology Criteria for Adverse Events; DLT = dose-limiting toxicity; GM-CSF = granulocyte–macrophage colony-stimulating factor; ULN = upper limit of normal.

a. Laboratory values that meet criteria listed in this table should be repeated and confirmed within 24 hours of the initial results being reported.

Intrasubject dose escalation: Once a subject has completed Cycle 3 at her assigned dose level of drug, intrasubject dose escalation will be allowed. No more than 2 dose escalations are allowed for any subject. Only subjects whose conditions have not progressed on treatment and did not have a dose reduction of either palbociclib or H3B-6545 because of AEs can escalate to the highest dose level that has completed DLT assessment and has been shown to be safe (no more than 1 DLT in 6 subjects). Subjects on the intrasubject dose escalation will *not* be included in the DLT analysis at the higher dose level.

Dose expansion: An additional 12 subjects will be treated at the MTD/RP2D to further characterize safety, tolerability, and PK and to provide preliminary estimates of efficacy. In Cycle 1, subjects will receive palbociclib PO QD on Days 1 to 21 and H3B-6545 PO QD on Days 9 to 28. In all subsequent cycles, palbociclib will be administered on Days 1 through to 21 and H3B-6545 will be administered Days 1 through to 28.

AEs will be managed by treatment interruption, dose reduction, and/or treatment discontinuation in accordance with the dose modification instructions outlined in the protocol. Treatment will continue until disease progression, development of unacceptable toxicity, or withdrawal of consent.

The data cutoff date for the primary analysis will be approximately 6 months after the last subject receives their first dose of study treatment. The end of study will be the last assessment for the last subject (eg, the last assessment for the last subject in the Extension Phase).

An overview of the study design and the decision rules for selection of the RP2D is presented in Figure 1.

Figure 1 Study Design and Selection of the Recommended Phase 2 Dose

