Grade 3	 Day 1 of cycle: Withhold drug, repeat complete blood cell count monitoring within 1 week. When recovered to Grade ≤2, start the next cycle at the same dose. Day 15 of first 2 cycles: Continue palbociclib at current dose to complete cycle and repeat complete blood cell count on Day 22. 	Withhold dose until recovery to Grade ≤2; resume drug at next lower dose
Grade 1 or 2	No dose adjustment is required	No dose adjustment is required
All other hematological toxicity		
Grade 4	Withhold dose until recovery to Grade ≤2; resume drug at next lower dose	No dose adjustment is required.
Grade 3	• Day 1 of cycle: Withhold drug, repeat complete blood cell count monitoring within 1 week. When recovered to Grade ≤2, start the next cycle at the same dose.	No dose adjustment is required.

Table 5Dose Modifications and Management Recommendation –Hematologic Toxicities
	• Day 15 of first 2 cycles: Continue palbociclib at current dose to complete cycle and repeat complete blood cell count on Day 22.	
Grade 1 or 2	No dose adjustment is required	No dose adjustment is required
Grade 3 neutropenia with fever ≥38.5 °C and/or infection	Withhold palbociclib until recovery to Grade ≤ 2 ; resume at the next lower dose	Withhold dose until fever subsides; resume at the same dose

CTCAE = Common Terminology Criteria for Adverse Events.

a. Laboratory values that meet criteria listed in this table should be repeated and confirmed within 24 hours of the initial results being reported.

b. Subjects who do not receive at least 75% of the dose for reasons other than toxicity (eg, withdrawal of consent, physician decision, lost to follow-up, etc.) will not be considered evaluable for DLT

Nonhematologic Toxicities

Table 6Dose Modifications and Management Recommendation –Nonhematologic Toxicities

CTCAE Grade	Palbociclib	H3B-6545
Sinus bradycardia		
Grade 1 (asymptomatic) Heart rate ≥40 bpm	No dose adjustment is required	No dose adjustment is required
Grade 1 (asymptomatic) Heart rate <40 bpm	No dose adjustment is required	First occurrence: Withhold drug until heart rate is ≥50 bpm; resume drug at the same dose level
		Second occurrence: Withhold drug until heart rate is ≥50 bpm; resume drug at the next lower dose
Grade 2 (symptomatic, intervention not indicated; change in medication initiated)	No dose adjustment is required	Withhold drug until (a) symptoms resolve and (b) heart rate is \geq 50 bpm; resume drug at the next lower dose

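### The intrasubject escalation rule screens for an AE-driven dose reduction but not for a DLT, so a subject with a DLT that needs no reduction may escalate

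*Protocol*

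**What the plan says.** The intrasubject escalation rule appears in the Synopsis (Study Design) and in Protocol Section 9.1, in nearly identical words. The Synopsis says that subjects without progression who "did not have a dose reduction of either palbociclib or H3B-6545 because of AEs can escalate to the highest dose level" that has cleared. Section 9.1 restricts escalation as follows: "Only subjects whose conditions have not progressed on treatment and did not have a dose reduction of either palbociclib or H3B-6545 because of AEs". The subject must also have completed Cycle 3 at her assigned dose. DLTs enter the rule once, as a property of the destination: the target level must have shown at most one DLT among six subjects.

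DLTs are assessed from "Cycle 1 Day 9 to Cycle 2 Day 8". Criteria relevant here are:

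- Grade 3 thrombocytopenia "lasting more than 7 days or associated with clinically significant bleeding";
- "Grade 3 or 4 serum creatinine";
- "Grade 3 or 4 bilirubin increase".

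Dose changes are set out separately in Section 9.5. For Grade 3 hematologic toxicity other than anemia, Table 5 says of palbociclib on Day 15 of the first two cycles: "Continue palbociclib at current dose to complete cycle and repeat complete blood cell count on Day 22". If the toxicity is present on Day 1 of a cycle, palbociclib is withheld, and then: "When recovered to Grade ≤2, start the next cycle at the same dose". H3B-6545 is not adjusted. In Table 6, the row for other nonhematologic events reduces both drugs for Grade 3 or 4 only when the event persists under optimal care.

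**The concern.** The rule uses dose reduction as its marker of intolerance. That works only if every DLT leads to a reduction or to stopping, and the protocol does not say so. Where the DLT table and the dose-modification tables diverge, a subject can be the one permitted DLT in her cohort, stay at full dose, and later qualify for more drug.

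The rule can also rank events the wrong way round. Grade 3 anemia is not on the hematology DLT list, yet Table 5 reduces H3B-6545 for it. Grade 4 neutropenia that recovers to Grade 2 or better within 7 days is not a DLT, yet Table 5 reduces palbociclib. Both subjects are barred from escalating, while one with a formal DLT may not be.

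The step can be large, because escalation goes to the highest cleared level, not the next one. From Cohort 1 (palbociclib 100 mg, H3B-6545 300 mg) to Cohort 3 (125 mg, 450 mg) it is 125/100 = +25% for palbociclib and 450/300 = +50% for H3B-6545. What is at stake is the safety of a few subjects, not the MTD estimate: escalated subjects are left out of the DLT analysis at the higher level.

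**Working it through.** The plan gives no figure to reproduce; Section 9.8.2 states that no formal sample size calculation was done. The check is textual, followed by an estimate of reach.

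**Clear case: Grade 3 thrombocytopenia lasting more than 7 days**

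1. Table 8 schedules blood counts on Cycle 1 Days 15, 21 and 28 and Cycle 2 Days 1 and 8, all inside the DLT window.
2. Suppose platelets are Grade 3 on Day 15. Table 5 continues palbociclib at the same dose.
3. Suppose they are still Grade 3 on Day 28. The duration is 28 − 15 = 13 days, which exceeds 7, so this is a DLT. Palbociclib dosing ended on Day 21, so no palbociclib decision arises until Cycle 2 Day 1.
4. On Cycle 2 Day 1, Table 5 withholds palbociclib and restarts it at the same dose after recovery. H3B-6545 is unchanged.
5. No reduction has occurred. If she completes Cycle 3 without progression or a later reduction, she meets every written condition.

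**Narrower case: Grade 3 nonhematologic DLTs**

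Grade 3 creatinine, Grade 3 bilirubin and most other Grade 3 nonhematologic events are DLTs without a duration condition. Table 6 reduces the dose only if the event persists. One that resolves with care is a DLT without a reduction.

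**Events outside the gap**

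- Grade 4 neutropenia, Grade 4 thrombocytopenia and Grade 3 neutropenia with fever reduce palbociclib (Table 5).
- Grade 3 bradycardia and Grade 3 QTcF prolongation reduce both drugs (Table 6).
- Combined ALT/AST and bilirubin elevation is a stopping criterion (Section 9.3.3).
- Intolerable toxicity leads to discontinuation (Section 9.6.5).

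**Reach**

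A cleared cohort holds at most one DLT subject in six. Cohort 3 is the top level, so only Cohorts 1 and 2 can supply an affected subject. Cohort 3b (100/450) is not counted as higher than Cohort 2 (125/300). Assume the same true DLT rate p at each level, with n = 6:

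- P1 = P(exactly 1 DLT) = 6p(1−p)^5
- C = P(at most 1 DLT) = (1−p)^6 + P1
- DLT subject in Cohort 1 with a higher cleared level: P1·C
- DLT subject in Cohort 2 with a higher cleared level: C·P1·C
- Both: P1·P1·C
- At least one: P1·C + C·P1·C − P1·P1·C

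| p | P1 | C | Cohort 1 | Cohort 2 | Both | At least one |
|---|---|---|---|---|---|---|
| 0.10 | 0.354 | 0.886 | 0.314 | 0.278 | 0.111 | 0.481 |
| 0.15 | 0.399 | 0.776 | 0.310 | 0.241 | 0.124 | 0.427 |
| 0.20 | 0.393 | 0.655 | 0.258 | 0.169 | 0.101 | 0.325 |

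Next, the subject must reach the end of Cycle 3 (Day 84) without progression. With the monotherapy median PFS of 5.3 months (Section 7.2.1) and an exponential curve, this is exp(−ln 2 × (84/30.4375)/5.3) = 0.697.

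Let f be the share of DLTs managed without a reduction, and q = 0.697·f. The chance of at least one affected subject is (Cohort 1 + Cohort 2)·q − Both·q²:

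| p | f = 1 | f = 0.5 | f = 0.25 |
|---|---|---|---|
| 0.10 | 0.358 | 0.193 | 0.100 |
| 0.15 | 0.324 | 0.177 | 0.092 |
| 0.20 | 0.248 | 0.136 | 0.071 |

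The documents give neither p nor f, so both are assumptions.

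**The case against.** There are five arguments on the other side.

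- **Discretion.** Section 9.5 presents Tables 5 and 6 as recommendations under the physician's judgment, and escalation is permitted, not required. A physician may reduce after a DLT, which triggers the existing bar, or may simply decline to escalate. This stands and lowers the risk, but discretion is not a bar, and the protocol already chose a fixed AE-based condition for this decision.
- **Section 9.6.5.** It lists drug-related abnormal laboratory values among the reasons to stop, and the named examples are laboratory values. Read to cover every such value, that line would contradict Table 5, which resumes dosing after Grade 3 and 4 counts. The workable reading is irreversible or intolerable values, and that leaves the gap open.
- **Demonstrated tolerance.** The DLT window closes on Cycle 2 Day 8 (Day 36), so she will have gone 84 − 36 = 48 further days without a reduction. The ceilings are also known doses: 125 mg is the usual palbociclib starting dose and 450 mg is the H3B-6545 monotherapy RP2D. This is a fair reason to call the risk limited. It shows tolerance of her current dose, not of a higher one.
- **The narrower case.** Laboratory DLTs should be confirmed within 24 hours, and whether an event persists is a clinical judgment. The size of this group is unknown, and the point stands.
- **The percentages.** They count all DLTs and then apply an unsourced share. They also ignore later reductions in Cycles 2 and 3, and whether a higher level clears while she is still on treatment. For the clear case, the monotherapy table shows a Grade 3 thrombocytopenia entry of 3 at 100–300 mg and 0 at 450 mg. The figures should be read as bounds and illustrations, not estimates.

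**Conclusion.** The concern holds. As written, the rule admits a subject with a formal DLT to a higher dose. This follows directly from the tables for Grade 3 thrombocytopenia lasting more than 7 days, and conditionally for Grade 3 nonhematologic DLTs that resolve with care. The gap is in the text and does not depend on the probabilities.

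Its practical size is small: at most about two subjects, with an upper bound of 36%, 32% or 25% for at least one affected subject at DLT rates of 10%, 15% or 20%. If half of DLTs need no reduction, the chance is 19%, 18% or 14%; if a quarter, 10%, 9% or 7%. These figures assume equal DLT rates across levels and exponential PFS at the monotherapy median. The consequence is for subject safety only. It should be corrected because safety and tolerability are the primary objective and the correction is cheap.

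**What to change.** In the escalation sentence of the Synopsis and of Section 9.1, insert the condition *did not experience a DLT* between the progression condition and the dose-reduction condition.

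The cost is one clause in two places. About one subject in each of Cohorts 1 and 2 at most would lose an optional escalation. The MTD rule, the DLT analysis and the sample size stay as they are, and the SAP needs no change, since its Section 3.2 refers to Protocol Section 9.1 for intrasubject escalation.
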